## 385 **4 STATISTICS AND METHODOLOGY**

### 386 **4.1. Statistical analysis plan**

387 Patients characteristics regarding to age, gender, pharmacological treatment, medical  
388 diagnosis will be analyzed exploratively/ descriptively.

389

#### 390 **Primary outcome:**

391 The primary outcome (Lidocaine plasma level) of our study is explorative and not comparative,  
392 therefore no H0 or H1 are formulated no power analysis is performed and only descriptive/  
393 explorative statistics are reported.

394 We plan to include 10 patients with complete data sets, meaning, full data of three infusions with  
395 stable dose of lidocaine (4mg/kg/BW) and escalating dose of ketamine (0.15 – 0.5mg/kg/BW).  
396 This corresponds to thirty measures of lidocaine plasma concentrations at a dose of 4mg/kg/BW).  
397 Patients without full data sets will be replaced but data from patients with preliminary study  
398 termination will be reported in the final protocol.

399

#### 400 **Secondary outcomes:**

401 1. Ketamine plasma levels are assessed according to lidocaine levels.

402

403 2. H0: dose escalation of ketamine has no effect on pain (outcome measure: SF-MPQ-2) and  
404 mood (outcome measure: BDI-II. H1: we hypothesize that ketamine dose has an effect on both  
405 outcome measures. For repeated measurements, an ANOVA will be separately calculated for  
406 outcome measures of pain and mood as dependent variable. This analysis will be performed  
407 separately for intermediate (one and two weeks) and long term effects (four weeks). For  
408 comparative outcomes a level of significance of 0.05 will be used. In case of multiple testing, a  
409 correction factor (in case of ANOVA: Bonferroni) for multiple testing is applied.

410

411 3. Side effects during treatment will be primary analyzed descriptively.

412

413 4. Multiple exploratory linear regressions will be calculated to evaluate the impact of dose and  
414 plasma levels of lidocaine and ketamine on pain and mood as well as occurrence of side-effects.

415

416 SPSS Version 25 will be used for data analyzation and graph pad PRISM Version 9 for data  
417 visualization. The investigators, [name] and [name], will perform all analysis  
418 steps. If needed, statistical guidance will be applied by statisticians of the Clinical Trial Unit (CTU)  
419 of the USB.

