Statistical Considerations:	
Patients characteristics regarding to age, gender, pharmacological treatment, medical diagnosis will be analyzed exploratively/ descriptively.
 
Primary outcome:
 
The primary outcome (Lidocaine plasma level) of our study is explorative and not comparative, therefore, no H0 or H1 are formulated no power analysis is performed and only descriptive/ explorative statistics are reported.
 
We plan to include 10 patients with complete data sets, meaning, full data of three infusions with stable dose of lidocaine (4mg/kg/BW) and escalating dose of ketamine (0.15 – 0.5mg/kg/BW). This corresponds to thirty measures of lidocaine plasma concentrations at a dose of 4mg/kg/BW). Patients without full data sets will be replaced but data from patients with preliminary study termination will be reported in the final protocol.
 
Secondary outcomes:
 
 
1. Ketamine plasma levels are assessed according to lidocaine levels.
 
2. H0: dose escalation of ketamine has no effect on pain (outcome measure: SF-MPQ-2) and mood (outcome measure: BDI-II. H1: we hypothesize that ketamine dose has an effect on both outcome measures. For repeated measurements, an ANOVA will be separately calculated for outcome measures of pain and mood as dependent variable. This analysis will be performed separately for intermediate (one and two weeks) and
 

	
long term effects (four weeks). For comparative outcomes a level of significance of 0.05 will be used. In case of multiple testing a correction factor (in case of ANOVA: Bonferroni) for multiple testing is applied.
 
3. Side effects during treatment will be primary analyzed descriptively.
 
4. Multiple exploratory linear regressions will be calculated to evaluate the impact of dose and plasma levels of lidocaine and ketamine on pain and mood as well as occurrence of side-effects.
 
SPSS Version 25 will be used for data analyzation and graph pad PRISM Version 9 for data visualization. The investigators, [name] and [name], will perform all analysis steps. If needed, statistical guidance will be applied by statisticians of the Clinical Trial Unit (CTU) of the USB.
 
Handling of missing data:
 
Dropouts will be replaced. We do not plan data imputation.

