189 of our infusion therapies, we increase the ketamine dose from 0.15mg/kg at the first infusion to  
190 0.25mg/kg at the second infusion and 0.5mg/kg at the third infusion. In cases where patients  
191 already experiencing sufficient analgesic effect and/or improvement in quality of life after the 1st  
192 or 2nd infusion or if side effects are not tolerated, no further increase of ketamine dosage is made.  
193 Therefore, another aim of this study is to investigate whether higher plasma levels of ketamine  
194 can be correlated with a better analgesic effect.

195

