### 339 3.3.2 Standard Procedure of lidocaine-ketamine infusions at the Pain Unit of USB

340  
341 During a short medical history interview Patients are briefly asked about their current pain  
342 situation before each infusion. For safety reasons, additional questions are asked about weight  
343 changes, compliance with fasting (= no solid food for 6 hours, no drinks for 2 hours) and allergies.

344 Monitoring is then installed (10-minute blood pressure measurement, continuous SPO2 and 5-  
345 lead ECG are recorded) and venous access is established. Lidocaine and ketamine are infused  
346 over a period of 30 minutes. The dosage of lidocaine is 4mg/kg is maintained throughout the  
347 infusions, and the dosage of ketamine is increased within the first three infusions from 0.15mg/kg  
348 at the first, to 0.25mg/kg at the second and 0.5mg/kg at the third infusion. In case patients already  
349 experiencing sufficient analgesic effect and/or improvement in quality of life after the 1st or 2nd  
350 infusion or if side effects do not allow a further dose increase, no further step up of ketamine  
351 dosage is made. We define a sufficient effect as a significant pain reduction (more than 50%) for  
352 at least 2 weeks and/or better quality of life with improved functionality during at least 2 weeks.

353 After the infusion, patients are monitored for at least another half hour, are discharged in company  
354 and are instructed to not run heavy machines and motor vehicles for at least 24 hours.

355

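### The only formal hypothesis test (section 4.1, secondary outcome 2) is worded as a ketamine-dose effect, which this design cannot separate from infusion order or earlier response

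*Protocol*

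**What the plan says.** Section 4.1, secondary outcome 2, gives the null as "H0: dose escalation of ketamine has no effect on pain (outcome measure: SF-MPQ-2) and" mood measured by BDI-II. The synopsis gives the alternative in the same terms as section 4.1: "H1: we hypothesize that ketamine dose has an effect on both outcome measures". The method is stated as "For repeated measurements, an ANOVA will be separately calculated for" pain and mood. It is run separately for the one- and two-week window and the four-week window, at 0.05, with Bonferroni where several tests are made.

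Section 3.3.2 fixes how dose is assigned: "infusions, and the dosage of ketamine is increased within the first three infusions from 0.15mg/kg" at the first infusion to 0.25 mg/kg at the second and 0.5 mg/kg at the third, with lidocaine held at 4 mg/kg. The exception covers patients with sufficient effect after infusion 1 or 2: "infusion or if side effects do not allow a further dose increase, no further step up of ketamine" dosage is made in those cases, or where tolerability prevents it. Section 1 says the same: "if side effects are not tolerated, no further increase of ketamine dosage is made". Sufficient effect is defined by the patient's own earlier course (more than 50% pain reduction for at least two weeks and/or better quality of life with improved functionality).

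Section 2.3 describes a single-centre observational pilot. Random selection in section 3.1 refers to choosing patients, not doses. The complete data set, in the synopsis and in section 4.1, is defined as "full data of three infusions with stable dose of lidocaine (4mg/kg/BW) and escalating dose of ketamine", and patients without full data are replaced.

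**The concern.** The hypothesis names a cause (ketamine dose), while the planned test compares occasions (infusions 1, 2 and 3). In a patient who escalates as planned, these are the same factor. In a patient who does not, dose is a consequence of the earlier outcome or of side effects. Neither group gives a contrast in dose that is free of time, cumulative lidocaine, carry-over from earlier infusions and regression to the mean. Regression to the mean is a live possibility in people newly referred for treatment-refractory pain.

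This is the only H0/H1 pair in the protocol, since section 4.1 says none is formulated for the primary lidocaine outcome. Sections 6.1 and 6.2 say the results should inform dose adjustment and optimised infusion regimens. As worded, rejecting H0 means accepting that ketamine dose matters, whatever produced the difference between infusions.

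A connected problem is that the complete-data definition includes an escalating ketamine dose. It is unclear whether a patient with three infusions and no escalation is complete or is to be replaced. Replacing such patients would select the sample on response or tolerance.

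**Working it through.** The protocol states no effect size, SD or power for this test, so there is no figure of its own to reproduce. Two things can be checked: whether a dose effect can be estimated, and what the ANOVA does when there is none.

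**1. Can dose be separated from infusion number?**

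Inputs: 10 complete patients with three infusions each (section 4.1); doses 0.15, 0.25 and 0.5 mg/kg (section 3.3.2).

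- All 10 escalate: 10 patient columns + 2 infusion columns = rank 12. Adding a dose column gives 13 columns, still of rank 12. Dose is an exact function of infusion number and adds nothing.
- If 1, 2 or 3 of the 10 stay at 0.25 mg/kg at infusion 3, the rank becomes 13. A dose term can then be estimated, but only through those patients, whose dose was set by earlier response or side effects.

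**2. Does response-dependent dosing bias the dose contrast?**

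Assumed values: pain mean 6, SD 2, correlation 0.5 between occasions, no drug effect at all, and escalation stopped once pain has fallen by at least 50%. Simulated mean pain at infusion 3 by dose received:

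| Ketamine dose at infusion 3 (mg/kg) | Mean pain |
|---|---|
| 0.15 | 4.8 |
| 0.25 | 4.9 |
| 0.5 | 6.1 |

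Higher dose appears to go with more pain although nothing has any effect.

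**3. How often is the null rejected when dose does nothing?**

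Assumed model: raw scores, one value per infusion, n = 10, k = 3, and a steady drift d per infusion unrelated to dose. The infusion means are −d, 0 and +d around their average, so the noncentrality is

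ncp = n × (d² + 0 + d²) / SD² = 20 × (d/SD)², with degrees of freedom k − 1 = 2 and (n − 1)(k − 1) = 18.

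SD is the within-patient SD. The level 0.0125 is 0.05/4, counting two outcomes and two windows.

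| d/SD | ncp | 0.05 | 0.025 | 0.0125 |
|---|---|---|---|---|
| 0.25 | 1.25 | 0.138 | 0.081 | 0.047 |
| 0.5 | 5.0 | 0.436 | 0.316 | 0.221 |
| 0.75 | 11.25 | 0.793 | 0.685 | 0.568 |
| 1.0 | 20.0 | 0.965 | 0.927 | 0.869 |

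For example, with SD 1.2 and drift 0.5 or 1.0 point per infusion, ncp = 3.47 or 13.89, and rejection at 0.05 is 0.316 or 0.874. A simulation of 40,000 runs at SD 1.2 gave 0.315 and 0.870, and 0.049 with no drift.

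Only the ratio d/SD matters, so the table applies to any scale. Bonferroni lowers the rates but does not address the problem, which is attribution and not multiplicity.

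**The case against.** The strongest reply is that the ANOVA is a valid test of differences between infusions. In this unit escalation simply is the step-up over infusions 1 to 3, so comparing infusions is the natural way to examine it in a 10-patient pilot. Its error rate is nominal when nothing changes. That is correct, and it is why the wording needs changing and the method does not. The exploratory label does not rescue the wording: the protocol attaches it to the primary outcome and to the regressions in item 4, while item 2 carries H0, H1, a significance level and a multiplicity rule.

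Second, the protocol does not say whether raw or change scores enter the ANOVA. Both questionnaires are completed directly before each infusion, so change from the pre-infusion score is available, and a steady linear drift then cancels. In the SD 1.2 scenario, simulated rejection falls to about 5%, against 32% and 87% for raw scores. This stands as a limit on the percentages above. It does not remove carry-over, cumulative lidocaine or regression to the mean, none of which need follow a straight line.

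Third, the model uses one value per infusion although the intermediate window has two, and the count of four tests is an inference. Both affect the illustration only.

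Fourth, the complete-data wording may be meant harmlessly: section 2.2 accepts any ketamine dose from 0.15 to 0.5 mg/kg for the primary endpoint, and not escalating is part of standard procedure. That supports counting these patients as complete, but the text should say so.

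**Conclusion.** The concern holds. The repeated-measures ANOVA tests whether scores differ between infusions. The stated H0/H1 concern a ketamine-dose effect, which this design cannot isolate. For full escalators this is exact (rank 12 with or without dose) and rests on no assumed value. For the others, any dose contrast rests on patients selected by outcome or tolerability.

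The size of the possible misattribution is not known from the protocol. On raw scores with an assumed drift of 0.25 to 1.0 within-patient SD per infusion, it runs from 14% to 97% at 0.05 and from 5% to 87% at 0.0125. With change scores and a purely linear drift it is about 5%.

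The primary lidocaine outcome is descriptive and unaffected, and item 4 is already labelled exploratory. This should be fixed before analysis, but it does not undermine the study.

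**What to change.** In the synopsis and in section 4.1, replace only the two hypothesis sentences of item 2:

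- *H0: within each time window, SF-MPQ-2 and BDI-II scores do not differ across infusions 1 to 3. H1: they differ.*

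Then add:

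- *Ketamine dose follows infusion number and earlier response or tolerability, and there is no comparator. Neither this test nor the dose terms in item 4 will be interpreted as a causal ketamine-dose effect.*

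Keep the ANOVA, both time windows, the 0.05 level and the Bonferroni rule. Report scores by infusion together with the ketamine dose actually given, which section 3.3.1 already records.

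In both places that define a complete data set, state that patients with three infusions whose ketamine was not increased count as complete and are not replaced.

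Appendix 1 already supplies the data: days 7/14, 35/42 and 63/70 for the intermediate window, and days 28, 56 and 84 for four weeks after each infusion. Days 28 and 56 are also the pre-infusion assessments for infusions 2 and 3, so the text should say that they serve as the four-week values.

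The cost is a few sentences, with no new data, no new method and no change to treatment. The price is a weaker claim: a difference across infusions instead of a dose effect.

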## 223 3 PROJECT POPULATION AND STUDY PROCEDURES

### 224 3.1 Project population, inclusion and exclusion criteria

225  
226 For our pilot project on drug plasma levels in an ambulatory infusion regime, a total of max. 15  
227 patients (10 + Drop-out of 50%) newly receiving lidocaine-ketamine infusions at the USB will be  
228 randomly selected. To minimize selection bias (including only responders, or patients with less  
229 side-effects) and because we increase the ketamine dosage normally during the first 3 infusions,  
230 we will only include patients who are new to lidocaine/ketamine infusions.

231

232 Inclusion Criteria:

233 - Patient is a new recipient of lidocaine-ketamine infusions

- 234 - Patient is 18 years of age or older
- 235 - Patient is able to provide Informed Consent
- 236
- 237 Exclusion Criteria:
- 238 - Contraindication to blood sampling (on arm not used for infusion)
- 239 - Insufficient knowledge of German language
- 240 - Inability to give consent
- 241 - Patient is under 18 years of age
- 242 - Contraindication to treatment with lidocaine and/or ketamine
- 243

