### 420 **4.2. Handling of missing data**

421 Dropouts will be replaced (c.f. 3.4). We do not plan data imputation.

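### In the week 1–2 analysis, a repeated-measures ANOVA without imputation drops a patient who misses one of six home forms; a mixed model in the planned software would keep the remaining scores

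*Protocol*

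**What the plan says.** - **Test.** Section 4.1, Secondary outcomes, item 2, states a null and an alternative hypothesis on ketamine dose escalation and says: "For repeated measurements, an ANOVA will be separately calculated for" pain (SF-MPQ-2) and mood (BDI-II). The synopsis says the same: "For repeated measurements, an ANOVA will be separately calculated for outcome measures of pain and mood as dependent variable". Weeks one and two are analysed apart from week four. On error rate: for "comparative outcomes a level of significance of 0.05 will be used", with Bonferroni correction for multiple testing.
- **Missing data.** Section 4.2: "Dropouts will be replaced (c.f. 3.4). We do not plan data imputation".
- **Complete data sets.** Section 4.1, Primary outcome: "We plan to include 10 patients with complete data sets, meaning, full data of three infusions with" a stable lidocaine dose and escalating ketamine, which the protocol equates with thirty lidocaine measurements. It continues: "Patients without full data sets will be replaced but data from patients with preliminary study" termination are to be reported.
- **Enrolment.** Section 3.1 allows at most 15 "patients (10 + Drop-out of 50%) newly receiving lidocaine-ketamine infusions".
- **Withdrawn patients.** Section 3.4 says that, unless the patient asks otherwise, data gathered up to withdrawal are still evaluated.
- **Forms.** Section 3.3 and Appendix 1 place both questionnaires immediately before each infusion, 7 and 14 days after each infusion, and 28 days after the third. Forms between visits are completed through an e-mailed link, on paper for the BDI-II, or by telephone with study staff if the patient wishes.

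**The concern.** The protocol does not mention listwise deletion, but that is what a standard repeated-measures ANOVA does when a cell is empty and nothing is imputed. The week 1–2 analysis depends wholly on forms completed away from the clinic, where an occasional missed form is to be expected. A patient who attends all three infusions and returns five of six pain forms would contribute nothing to the week 1–2 pain ANOVA.

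Two things are at stake. The first is precision: the trial's only formal hypothesis test could rest on clearly fewer patients than were followed. The second is bias: patients who return every form may differ from those who do not, and a complete-case analysis needs a stronger assumption about missingness than a likelihood-based model does. The method also sits badly with section 3.4, because the named ANOVA cannot evaluate the partial series of a withdrawn patient.

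**Working it through.** **The plan's own figure.** 10 + 50% of 10 = 15, the stated maximum. There is no power or sample-size figure for the ANOVA to reproduce.

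**Inputs from the protocol.** Three infusions; forms on days 7 and 14 after each; target 10 patients with complete infusion data; maximum 15; no imputation. Cells per outcome in the week 1–2 ANOVA: 3 × 2 = 6.

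**Assumed input.** The share of forms missing, m, is not in the protocol. I use 5%, 10% and 20%.

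**Independent missingness.** P(all six present) = (1 − m)^6.

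| m | (1 − m)^6 | of 10 patients | of 15 patients |
|---|---|---|---|
| 5% | 0.95^6 = 0.735 | 7.4 | 11.0 |
| 10% | 0.90^6 = 0.531 | 5.3 | 8.0 |
| 20% | 0.80^6 = 0.262 | 2.6 | 3.9 |

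The 15-patient column is a best case. The extra five places are there for drop-outs, and a patient who leaves before the third infusion cannot have six cells.

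**Share of collected scores lost to this ANOVA.** Patients with full series hold 6(1 − m)^6 of the expected 6(1 − m) scores per patient, so the share lost is 1 − (1 − m)^5: 23%, 41% and 67%.

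**Clustered missingness.** Let the missing rate vary between patients (beta-binomial) with within-patient correlation 0.3, also assumed. With s = (1 − 0.3)/0.3 = 2.333 and a = (1 − m)s, P(all six present) is the product over i = 0 to 5 of (a + i)/(s + i).

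- m = 5%: 0.950 × 0.965 × 0.973 × 0.978 × 0.982 × 0.984 = 0.84
- m = 10%: 0.900 × 0.930 × 0.946 × 0.956 × 0.963 × 0.968 = 0.71
- m = 20%: 0.800 × 0.860 × 0.892 × 0.913 × 0.926 × 0.936 = 0.49

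That is 8.4, 7.1 or 4.9 of 10 patients, and 12.6, 10.6 or 7.3 of 15.

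**Four-week analysis.** It draws on days 28, 56 and 84. Days 28 and 56 are completed at the clinic just before infusions 2 and 3. If those are complete, only day 84 is exposed, and 95%, 90% or 80% of patients are kept. A missed day 7 or day 14 form has no effect here.

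**What a mixed model keeps.** A likelihood-based model uses every score collected, so the share lost is 0% at any m.

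**The case against.** The strongest reply is that this is an unpowered secondary test in a pilot of about ten patients whose primary outcome is descriptive, and that the size of the loss depends on a missing rate that nobody knows. The telephone option should also help completion. At 5% missing, or with clustered missingness, the loss is moderate. All of this stands, and it limits the weight of the point. It is not a reason to keep a method that discards collected scores when another is available at no cost.

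Four stronger readings are tempting and are not supported:

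- **That the replacement rules clash and 15 patients cannot yield 10 complete ones.** A reader might infer this by taking full data to include every questionnaire. But the definition stands under the primary outcome, refers to three infusions, and is equated with thirty lidocaine measurements (10 × 3). On that natural reading a missed questionnaire triggers replacement nowhere, and the rules agree. The consequence is only that replacement does not top up the ANOVA.
- **That partial data go to waste.** Section 3.4 has them evaluated, section 4.1 has early terminators reported, and the regressions in item 4 do not require all six forms. The loss is confined to the ANOVA.
- **That one missed form removes a patient altogether.** Pain and mood are tested separately, and so are weeks 1–2 and week 4.
- **That a mixed model removes bias.** It does so only if data are missing at random. If a form is missed because of how the patient feels that week, and earlier scores do not reveal this, the mixed model is biased too. Nor does it separate ketamine dose from infusion order: section 3.3.2 allows escalation to be withheld for sufficient effect or for side effects.

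**Conclusion.** The point holds as an improvement to a secondary analysis. The protocol fixes a method that, without imputation, excludes a patient from the week 1–2 ANOVA of an outcome when one of six home forms for that outcome is missing. At 5%, 10% or 20% of forms missing, the share of patients kept is 74%, 53% or 26% under independence, and 84%, 71% or 49% with a within-patient correlation of 0.3. These figures rest on assumed missing rates, an assumed correlation, and the reading that weeks 1 and 2 enter one ANOVA. If each week were tested alone, three cells would be needed and (1 − m)^3 = 86%, 73% or 51% would be kept under independence. The direction is the same throughout. The primary outcome is unaffected.

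**What to change.** 1. **Section 4.1 item 2 and the synopsis.** Replace the ANOVA by a linear mixed model for each outcome (MIXED in the SPSS already planned): random patient intercept, fixed effects for infusion and week, and a small-sample degrees-of-freedom correction such as Satterthwaite. Use all available scores from every patient with at least one post-infusion score, including drop-outs and replaced patients, subject to the patient's right under section 3.4 to ask otherwise.
2. **Same place.** State that the model is valid if data are missing at random, and that infusion number is not the same as ketamine dose because escalation may be withheld.
3. **Section 4.2.** State that replacement concerns the three-infusion plasma data and is not triggered by a missed questionnaire. No imputation is needed.

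The cost is a few sentences, with the same software and the same data. There is a small downside: with 10 to 15 patients the degrees of freedom are approximate and the covariance structure must stay simple. A random intercept assumes equal correlation between all of a patient's scores over about ten weeks.
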